10.1.1 Demographic and Background Characteristics

The study population will be described in terms of general and background characteristics using usual statistics as mean, median, standard deviation and range for continuous variables and frequencies for categorical variables. Study conduct will also be evaluated by an accurate description of protocol deviations, treatment administration and study completion status.

10.1.2 Laboratory Variables

The normal ranges of the local laboratory, including those for liver enzymes, will be used as the normal ranges for the respective subject. All laboratory data will be converted in the International System of Units (SI units) for the analysis, with the exception of the liver enzyme values. For the liver enzymes ALT and AST, the unit U/L will be used. The NCI-CTCAE v4.0 grading system will be used for assessing laboratory abnormalities.

Ibrutinib + GA101 – Obinutuzumab. University of California, San Diego

10.1.3 Concomitant Medications

The use of concomitant medications will be recorded at each visit and described using descriptive statistics.

10.1.4 Estimated Time to Complete Enrollment

The estimated time of accrual of the total number of subjects is 24 months.

10.1.5 Data Analysis

The complete analysis of all study data will be contained in the clinical study report at the end of the study.

10.2 STATISTICAL CONSIDERATIONS FOR THE PHASE IB

The primary objective of the Phase Ib of this clinical study is to evaluate the safety, tolerability and DLT of Ibrutinib in combination with GA101 - Obinutuzumab.

10.2.1 Subject Evaluability for the Phase Ib

The first 6 subjects who receive at least one dose of Ibrutinib and/or GA101 – Obinutuzumab will be considered evaluable for safety, tolerability and DLTs.

10.2.2 Safety Analysis

All subjects who have at least one dose of Ibrutinib and/or one infusion of GA101 – Obinutuzumab, and a safety follow-up, whether withdrawn prematurely or not, will be included in the safety analysis.

10.2.3 Clinical Adverse Events

All adverse events, including unrelated adverse events, will be listed and graded according to the NCI-CTCAE grading system (Version 4.0) (Appendix 7). The proportion of subjects with treatment-related adverse events, overall, and by body system, will be tabulated. In addition, subjects with treatment-related adverse events, SAEs, and adverse events leading to withdrawal will be listed overall and, if appropriate, distributions by body system will be provided.

10.2.4 Definition of Dose Limiting Toxicity (DLT)

Dose limiting toxicity (DLT) is defined as any of the adverse events (AEs) noted below that are considered by the investigator to be possibly related or related to Ibrutinib / GA101 - Obinutuzumab treatment. For the purpose of defining DLTs, AE will be tabulated and assessed based on the signs and symptoms present during the first cycle of treatment (Day 1 - 28). Toxicity will be graded according to the NCI-Common Terminology Criteria for Adverse Events (CTCAE) version 4.0 (Appendix 7) except for hematological toxicities that will be graded according to the IWCLL guidelines (Hallek et

Ibrutinib + GA101 - Obinutuzumab. University of California, San Diego

al., 2008) (Appendix 3) For subjects with a normal neutrophil count, platelet count, and/or hemoglobin value at baseline, the NCI-CTCAE v4.0 grading system will be used. Dose limiting toxicity will include possibly related or related events that are Grade ≥ 3 that do not resolve to Grade ≤ 1within 14 days of initiation despite appropriate medical management. The following exceptions will apply:

Non Hematologic:

- ≥ Grade 3 nausea, vomiting, or diarrhea only if uncontrolled by maximal antiemetic/antidiarrheal therapy.

Hematologic:

Hematologic toxicity will be graded according to the IWCLL guidelines (Hallek et al., 2008) - (Appendix 3), with dose-limiting hematologic toxicity defined as follows:

- ≥ Grade 4 granulocytopenia lasting ≥ 14 days. Note that per IWCLL guidelines, subjects are evaluable for toxicity related to granulocytopenia only if the pre-treatment ANC is >1.0 x10⁹/L.
- ≥ Grade 4 thrombocytopenia lasting ≥ 14 days or thrombocytopenia associated with bleeding. Note that per IWCLL guidelines, subjects are evaluable for toxicity related to thrombocytopenia only if the pre-treatment platelet count is >20,000/µL.
- Grade \geq 3 infusion-related reactions to GA101 Obinutuzumab will be considered DLTs under the following circumstances:
 - If subjects experience Grade 3 infusion-related reactions at re-challenge despite appropriate medical management that leads to permanently discontinue GA101 – Obinutuzumab.
 - Any Grade 4 infusion reactions, including but not limited to anaphylaxis, acute life-threatening respiratory symptoms, or other life-threatening infusion reaction.

10.2.5 Dose Escalation / De-escalation Based on AE - DLT

Dose modifications or discontinuation actions for Ibrutinib are described in table 4 (see section 6.3.1). No dose escalation or de-escalation will occur for GA101 – Obinutuzumab. If a subject experiences grade 3 or 4 cytopenia, the guidelines for Ibrutinib and GA101 – Obinutuzumab dose-delay are outlined in table 7 (Section 6.3.4).

Ibrutinib + GA101 - Obinutuzumab. University of California, San Diego

10.2.6 Statistical Operating Characteristics of the Phase IB

The phase IB will be performed as a safety run-in with the first 6 subjects enrolled in the study. The sample size of 6 subjects is considered to be sufficient to support preliminary safety, tolerability and DLTs assessments (Goede et al., 2013). On this group of subjects, we will evaluate safety, tolerability and dose-limiting toxicities (DLTs) during the first cycle of treatment (4 weeks; Day 1 - 28),

Subjects will be enrolled at least one week apart to avoid overlapping time of observation during the first week of treatment when infusion reactions are expected to be higher.

- If 0 to 1 DLTs (See DLT definition Section 10.2.4) are observed in the first 3 subjects, we will proceed to enroll 3 additional subjects.
- If 0 to 1 DLTs are observed in the first 6 subjects, we will proceed to the phase II of the study.
- If \geq 2 DLTs are observed, we will hold enrollment and revise the study design with the sponsor.

The table below gives the characteristics of this procedure. For a range of underlying dose limiting toxicity rates, the probability that the study will be stopped during the Phase IB (i.e. the probability that there are two or more DLT's within the first six subjects) and the expected number of DLT's are computed.

Table 8 Operating Characteristics of the Phase IB Procedure

Toxicity Rate	Probability of Halting	Expected # Toxicities
5%	3.3%	0.3
10%	11.4%	0.59
15%	22.4%	0.87
20%	34.5%	1.14
25%	46.6%	1.38
30%	58%	1.61
35%	68.1%	1.8
40%	76.7%	1.98
45%	83.6%	2.13
50%	89.1%	2.25

Thus, when the DLT rate is as high as 30%, the probability of stopping the trials will be at least 58%. Conversely, if the DLT rate is no more than 10%, then the chance of stopping the trials during this phase is at most 11.4%.

Ibrutinib + GA101 - Obinutuzumab. University of California, San Diego

10.3 STATISTICAL CONSIDERATIONS FOR THE PHASE II

The primary objective of the phase II stage of this clinical trial is to evaluate the overall response rate (partial responses + complete responses) in CLL subjects treated with Ibrutinib in combination with GA101 – Obinutuzumab.

All subjects who receive at least one dose of Ibrutinib and/or GA101 – Obinutuzumab will be considered evaluable for safety, tolerability and DLT.

10.3.1 Clinical and Laboratory Variables

Clinical and laboratory test will be tabulated after subjects have completed treatment under protocol.

10.3.2 Efficacy Population

The Efficacy Population includes all subjects who receive at least one dose of study drug and have baseline and at least one post-baseline efficacy assessment.

10.3.3 Efficacy Analysis

Response assessment will be performed by physical examination, CT scan evaluation and bone marrow biopsy/aspirate at completion of therapy using the International Workshop in CLL Guidelines (IWCLL) (Hallek et al., 2008) (See section 3.2.2). The ORR will be estimated with an exact 95% confidence interval (CI) for the combination regimen of Ibrutinib/GA101 – Obinutuzumab.

Median PFS, TFS and OS, and their 95% CI will be estimated using the Kaplan-Meier method.

10.3.4 Statistical Operating Characteristics of the Phase II

The sample size calculation has been made using a comparative overall response with GA101 – Obinutuzumab in combination with chlorambucil, which is a standard of care regimen for previously untreated CLL subjects. This combination regimen can induce an overall response rate (ORR) of 78% in CLL subjects (Goede et al., 2014). For the purpose of our sample calculation we will use a true ORR of 78% that will be tested against an alternative of 94%, which corresponds to the expected ORR that can be achieved when GA101 – Obinutuzumab is administered in combination with lbrutinib.

There is no data available using the combination of Ibrutinib and GA101 - Obinutuzumab, therefore we will use as a point of reference for the expected ORR, the recently published data of Ibrutinib in combination with Rituximab in relapse/refractory CLL subjects. In this publication the ORR was in the 90-95% range (Burger et al., 2013).

Ibrutinib + GA101 - Obinutuzumab. University of California, San Diego

Our sample size calculation will use an ORR endpoint comparison based on the ORR achieved with the Ibrutinib and GA101 - Obinutuzumab combination. We hypothesize that Ibrutinib in combination with GA101 - Obinutuzumab would induce an ORR of 94%, which is 16% higher than the ORR observed in the study published by Goede et al. (Goede et al., 2014)

Based on this, we will use a Simon's two-stage optimal design in this study (Simon, 1989). The null hypothesis that the true overall response rate is 78% will be tested against a one-sided alternative. In the first stage, 10 subjects will be accrued. If there are 8 or fewer responses in these 10 subjects, the study will be stopped. Otherwise, 22 additional subjects will be accrued for a total of 32. The null hypothesis will be rejected if 29 or more responses are observed in 32 subjects. This design yields a type I error rate of 5% and power of 80% when the true response rate is 94%.

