GA101 - Obinutuzumab must be administered in a clinical setting (inpatient or outpatient) by IV infusion for up to 6 cycles (28-day cycles): on cycle 1, GA101 – Obinutuzumab will be administered 100 mg on day 1, 900 mg on day 2 and 1,000 mg on days 8 and 15. On Cycles 2-6, Day 1, 1,000 mg of GA101 - Obinutuzumab will be administered (See Table 1 – Section 6.2.6).

Statistical Methods

Refer to Section 10 for the complete and detailed Statistical rationale. For this open-label study, all demographic, disease and relevant clinical characteristics will be summarized using descriptive statistics. Continuous variables will be reported using appropriate measures of dispersion and central tendency (means, medians, ranges and standard deviations) while categorical variables (e.g., gender) will be summarized as number and percentage [proportions and 95% confidence intervals (CI)] of the total Registry cohort. Each phase of this study will be analyzed separately. All tables, figures and listings will therefore be separated by study phase.

Determination of the Sample size for the Phase IB

The phase IB will be performed as a safety run-in with the first 6 subjects enrolled in the study. The sample size of 6 subjects is considered to be sufficient to support preliminary safety, tolerability and DLTs assessments

Ibrutinib + GA101 – Obinutuzumab. University of California, San Diego

(Goede et al., 2013). On this group of subjects, we will evaluate safety, tolerability and dose-limiting toxicities (DLTs) during the first cycle of treatment (4 weeks; Day 1 - 28),

Subjects will be enrolled at least one week apart to avoid overlapping time of observation during the first week of treatment when infusion reactions are expected to be higher.

- If 0 to 1 DLTs (See DLT definition Section 10.2.4) are observed in the first 3 subjects, we will proceed to enroll 3 additional subjects.
- If 0 to 1 DLTs are observed in the first 6 subjects, we will proceed to the phase II of the study.
- If \geq 2 DLTs are observed, we will hold enrollment and revise the study design with the sponsor.

Determination of the Sample size for the Phase II

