3.1.1 Phase II

In the phase II we will determine response rate in all subjects that have received treatment. This study will enroll 32 subjects and the sample size has been calculated using a Simon two-stage design (Simon, 1989). In the first stage, 10 subjects will be enrolled. If 8 or fewer responses are observed at the end of this stage, then the study will be terminated for futility. If at least 9 responses are observed, an additional 22 subjects will be enrolled in a second stage, for a total of 32 subjects. If at least 29 responses are observed among the 32, then efficacy of the treatment will be concluded. For additional statistical considerations see section 10.3.4.

Response assessments will be evaluated based on the International Workshop in CLL Guidelines (IWCLL) (Hallek et al., 2008).

Ibrutinib + GA101 - Obinutuzumab. University of California, San Diego

The estimated accrual time from first to last subject enrolled in the study will be 24 months (including the safety run-in of the phase lb)

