10. STATISTICAL CONSIDERATIONS AND RATIONALE

10.1 STATISTICAL MODEL

For this open-label study, descriptive statistics will be calculated for demographic and baseline characteristics, clinical response variables, immunologic variables and safety data. Each phase of this study will be analyzed separately. All tables, figures and listings will therefore be separated by study phase.

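### Does the exact 95% confidence interval for ORR undercut the one-sided 29-of-32 decision rule?

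*Combined protocol and SAP*

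**What the plan says.** Section 10.3.3 (Efficacy Analysis) gives the primary endpoint one summary: "The ORR will be estimated with an exact 95% confidence interval (CI) for the combination regimen". It does not name the exact method or mention the two stages, and it gives the interval no part in judging efficacy.

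The decision is set elsewhere. Section 10.3.4 states: "The null hypothesis that the true overall response rate is 78% will be tested against a one-sided alternative". Ten subjects enter first. The study stops at 8 or fewer responses; otherwise 22 more are added. The final criterion is: "The null hypothesis will be rejected if 29 or more responses are observed in 32 subjects". Section 3.1.1 ties the conclusion to the same count: "If at least 29 responses are observed among the 32, then efficacy of the treatment will be concluded". The stated properties are a type I error of 5%, and power of 80% at a true rate of 94%.

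Two general statements show how the interval is meant. Section 10.1 says that "descriptive statistics will be calculated for demographic and baseline characteristics, clinical response variables, immunologic variables and safety data", so response is among the variables to be described. The Statistical Methods part of the synopsis likewise attaches 95% intervals to proportions as summaries.

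**The concern.** Readers often use a confidence interval as a test: if it contains the null value, the null is not rejected. On that reading, 10.3.3 and 10.3.4 can give opposite answers. The smallest winning result is 29/32, or 90.6%. The count rule then declares efficacy against 78%, yet the interval printed beside the result would have a lower limit of about 75% and would contain 78%.

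The study hypothesis is a higher response rate than the one seen in the CLL11 study, so 78% is the value a reader will look for in the interval. If the documents left open which statistic decides, or if one of the two were miscalibrated, the efficacy conclusion at the boundary would be in doubt. A team could also pick the more favourable statistic after seeing the data.

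**Working it through.** **Inputs.** From section 10.3.4: null rate 0.78, alternative 0.94, 10 subjects in Stage 1, continue at 9 or more responses, 22 more subjects, reject at 29 or more of 32. From section 10.3.3: exact 95% interval. Assumed, because the plan does not say: two-sided Clopper-Pearson, and exactly 32 analysed subjects.

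**1. The plan's own figures.** The trial rejects if Stage 1 gives 9 responses and Stage 2 at least 20, or if Stage 1 gives 10 and Stage 2 at least 19:

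P(reject | p) = P(X₁ = 9)·P(X₂ ≥ 20) + P(X₁ = 10)·P(X₂ ≥ 19), with X₁ ~ Bin(10, p) and X₂ ~ Bin(22, p).

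- p = 0.78: 0.2351 × 0.1081 + 0.0834 × 0.2542 = 0.0254 + 0.0212 = **0.0466**.
- p = 0.94: 0.3438 × 0.8576 + 0.5386 × 0.9602 = 0.2948 + 0.5172 = **0.8120**.

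The stated 5% and 80% are met. The first figure is also the two-stage p-value at 29/32.

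**2. The planned interval beside the rule.** The Clopper-Pearson lower limit at x/32 is the p that solves P(Bin(32, p) ≥ x) = 0.025.

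| Responses | Rule | Exact 95% lower limit | 78% inside? |
|---|---|---|---|
| 28 | do not reject | 71.0% | yes |
| 29 | reject | 75.0% | yes |
| 30 | reject | 79.2% | no |
| 31 | reject | 83.8% | no |
| 32 | reject | 89.1% | no |

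The interval at 29/32 is 75.0% to 98.0%. Across all totals from 9 to 32, interval and rule disagree only at 29.

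**3. Where the difference comes from.** There are two sources: the tail area (2.5% or 5%) and the Stage 1 gate, which the ordinary interval ignores. Lower limits at 29/32:

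| | 2.5% per tail | 5% per tail |
|---|---|---|
| Ordinary exact | 75.0% | 77.5% |
| Two-stage exact | 75.7% | 78.3% |

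The two-stage limits solve P(pass Stage 1 and total ≥ 29 | p) = 0.025 or 0.05. From the ordinary 95% limit, the gate alone adds 75.7 − 75.0 = 0.7 points and the tail area alone adds 77.5 − 75.0 = 2.5 points. The tail area is the larger part. Only the two together lift the limit above 78%. The ordinary one-sided tail, P(Bin(32, 0.78) ≥ 29), is 0.0567, which is why an ordinary 90% interval still contains 78%.

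**4. Is the interval itself valid?** The test here is coverage when the trial can stop after Stage 1. Taking Clopper-Pearson on 10 subjects if stopped and on 32 otherwise, for true rates from 0.600 to 0.994 in steps of 0.001, the lowest coverage is 0.9546. The interval delivers at least its nominal 95%.

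**5. How often the boundary total occurs.** P(total = 29 and Stage 1 passed) = P(X₁ = 9)·P(X₂ = 20) + P(X₁ = 10)·P(X₂ = 19).

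- p = 0.94: 0.0829 + 0.0553 = 0.1382, which is 0.1382 / 0.8120 = 17% of the trials that conclude efficacy.
- p = 0.90, the low end of the 90–95% range that section 10.3.4 cites: 0.1813, and 0.1813 / 0.5289 = 34%.
- p = 0.78: 0.0183 + 0.0122 = 0.0304.

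**The case for a change.** The strongest argument for acting is that 29/32 is no remote outcome. It is the smallest win, and at a true ORR of 90% about a third of winning trials would end there. Section 10.3.3 plans no p-value and does not say that the interval is not the criterion. A team that sees 29/32 and reaches for the usual remedy, an ordinary 90% interval, would still find 78% inside it (77.5%). A two-stage exact 90% interval agrees with the rule at every total from 9 to 32, and adding it costs two sentences.

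The arithmetic stands, and so does the observation that the method is unnamed. The inference does not. Sections 3.1.1 and 10.3.4 already fix, in advance and by count, what leads to a conclusion of efficacy, so nothing is left to choose after the data are in. The addition would also leave the 95% interval in place. At 29/32 the report would then print lower limits of 75.0% and 78.3% on either side of 78%, and would need a sentence to explain them. That sentence would serve as well without the second interval. The exact agreement also holds only for 10 + 22 subjects, whereas the efficacy population in 10.3.2 could give another denominator. What remains is a preference about presentation.

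**Conclusion.** The concern does not hold. The plan states one decision rule, that rule meets its stated error rates (4.66% against 5%, and 81.2% against 80%), and the 95% interval keeps its coverage under the two-stage design (at least 95.46% over the range checked). A two-sided 95% interval printed beside a one-sided 5% test is an ordinary convention. Such an interval can contain a null value that the test rejects, because the two answer at different error levels. Here that happens at one total, 29 of 32, with probability 13.8% at the planned alternative and 3.0% at the null. Even then the efficacy conclusion is the one the plan prescribes.

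This rests on 32 analysed subjects in stages of 10 and 22, and on reading the interval as two-sided Clopper-Pearson. The second assumption matters little at 29/32: Sterne and Blaker intervals also contain 78% (p-value at 78% is 0.0905 for both), as does the mid-p interval (lower limit 76.6%). The conclusion would change only if the plan made the interval a criterion for efficacy, and no section does.

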10.4 REPLACEMENT OF SUBJECTS

For the safety run-in, subjects will be replaced if they withdraw from the study prior to day 28 of the first cycle for any reason other than withdrawal due to toxicity, progressive disease (PD) or death.

In the phase II, up to 3 subjects will be allowed to be replaced if they have not completed treatment response assessment and, if they withdraw from the study for any reason other than toxicity, progressive disease (PD) or death.

10.5 TRIAL STOPPING AND HOLDING RULES BASED ON DLT AND LACK OF EFFICACY

The trial will be stopped or put on hold and the data will be reviewed with the sponsor for any of the following reasons:

- If there is ≥ 1 deaths that are considered to be related or possibly related to the study medications or procedures related to this clinical trial.
- If the efficacy endpoint is not reached at the end of treatment of the Stage I subjects based on Simon II Stage design (Section 10.3.4).
- If ≥ 2 DLTs are observed in the first 6 subjects treated under the phase IB study, we will hold enrollment and revise the study design with the sponsor (Section 10.2.6).
- If the study is put on hold, the decisions regarding continuation of treatment for any subjects who have already received therapy will be made on a case-by-case basis after discussion with the subject and the principal investigator. All subjects will be re-consented.

Ibrutinib + GA101 – Obinutuzumab. University of California, San Diego

 All subjects who were on treatment at the time study-stopping criteria were met will continue to be followed by the principal investigator for safety until the end of the study.

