8. CRITERIA FOR STUDY DISCONTINUATION

The study will be discontinued due to the following reasons:

- Lack of meeting statistical end point after Stage I accrual. See section 10.3.
- Excessive toxicity of the regimen with > 1 subject death that is considered related to the study medications.

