11.4.4.2 Follow-Up Information

Additional information may be added to a previously submitted report by any of the following methods:

- Adding to the original MedWatch 3500A report and submitting it as followup
- Adding supplemental summary information and submitting it as follow-up with the original MedWatch 3500A form
- Summarizing new information and faxing it with a cover letter including subject identifiers (i.e., D.O.B. initial, subject number), protocol description and number, if assigned, brief AE description, and notation that additional or follow-up information is being submitted (The subject identifiers are important so that the new information is added to the correct initial report)

Occasionally Pharmacyclics may contact the reporter for additional information, clarification, or current status of the subject for whom and AE was reported. For

Ibrutinib + GA101 – Obinutuzumab. University of California, San Diego

questions regarding SAE reporting, you may contact the Pharmacyclics Drug Safety representative noted above or the MSL assigned to the study. Relevant follow-up information should be submitted to Pharmacyclics Drug Safety as soon as it becomes available and/or upon request.

MedWatch 3500A (Mandatory Reporting) form is available at http://www.fda.gov/AboutFDA/ReportsManualsForms/Forms/default.htm.

11.4.5 Data Safety and Monitoring Board (DSMB)

A Data Safety Monitoring Board (DSMB) will review the safety data once the study is opened. Summary reports will be submitted to the DSMB as indicated below:

- After completion of Phase IB and prior to initiation of the Phase II.
- After the enrollment of the first 10 subjects in the Phase II, i.e., at the point at which the decision is made to proceed, or not, to the enrollment of the second 10 subjects.

The summary reports will be written in a standard DSMB report format and will be prepared by the study statistician.

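### After the six-subject run-in, a related death is the only pre-specified toxicity trigger, and no DSMB report is scheduled for the 22 second-stage subjects

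*Combined protocol and SAP*

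**What the plan says.** **Run-in.** Section 10.2.6 sets the pass rule: "If 0 to 1 DLTs are observed in the first 6 subjects, we will proceed to the phase II of the study". Section 10.5 gives the matching hold: "If ≥ 2 DLTs are observed in the first 6 subjects treated under the phase IB study, we will hold enrollment". Section 10.2.4 confines DLTs to Cycle 1: "AE will be tabulated and assessed based on the signs and symptoms present during the first cycle of treatment (Day 1 - 28").

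**Phase II.** Section 10.3 states that all subjects given at least one dose "will be considered evaluable for safety, tolerability and DLT". No threshold or action follows. The other triggers in Section 10.5 are one or more deaths related or possibly related to the study medications or trial procedures, and failure of the Stage I efficacy endpoint. Section 8 lists the Stage I endpoint and "Excessive toxicity of the regimen with > 1 subject death that is considered related to the study medications".

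**DSMB.** Section 11.4.5 schedules two summary reports. The first falls between Phase IB and Phase II. The second is timed "After the enrollment of the first 10 subjects in the Phase II", which the same sentence equates with the decision whether to go on. Neither has a toxicity criterion. That sentence gives the next group as ten subjects, whereas Section 10.3.4 gives 22. Holds under Section 10.5 are reviewed with the sponsor, and the DSMB is not named.

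**The concern.** Six subjects cannot exclude a high DLT rate, and Table 8 says so openly. That is acceptable in a run-in if later data can still raise a flag. Here the one non-fatal rule lapses after subject 6, although most subjects are treated after that: 26 of 32 if the run-in six count towards the 32, or 32 of 38 if they do not. The remaining numerical interim gate is driven by response, so an active but poorly tolerated combination would tend to pass it.

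Section 1.4 says that no data exist on this combination. It calls the two drugs' adverse events non-overlapping, yet Sections 1.2.4 and 1.3.4 list neutropenia, thrombocytopenia, infection and atrial fibrillation for both. A stated rule on accumulating non-fatal toxicity would therefore be useful in this trial.

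**Working it through.** **1. Reproduce Table 8.** The inputs are n = 6 and a hold at 2 or more DLTs (Sections 10.2.6 and 10.5). P(hold) = 1 − (1−p)^6 − 6p(1−p)^5. At p = 0.30 this is 1 − 0.1176 − 0.3025 = 0.580, against the printed 58%. Section 10.2.6 reads the table the same way: "when the DLT rate is as high as 30%, the probability of stopping the trials will be at least 58" per cent. All ten printed halting probabilities reproduce. So does the expected-toxicity column, as 3p + 3p × P(at most 1 DLT in the first 3). At 30% that is 0.9 + 0.9 × 0.784 = 1.606, printed as 1.61.

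**2. Chance of passing the run-in, and DLTs expected afterwards.**

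| True DLT rate p | P(hold) | P(pass) | Expected among the 22 (22p) |
|---|---|---|---|
| 10% | 11.4% | 88.6% | 2.2 |
| 20% | 34.5% | 65.5% | 4.4 |
| 30% | 58.0% | 42.0% | 6.6 |
| 40% | 76.7% | 23.3% | 8.8 |

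Over everyone treated after the run-in, the expected count at 30% is 26 × 0.30 = 7.8 if the six count in the 32, or 32 × 0.30 = 9.6 if they do not. The documents do not settle which applies.

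**3. What the response gate adds.** Stage I stops at 8 or fewer responses in 10. That has probability 11.8% at an ORR of 94% and 68.2% at 78%. Assume that DLT and response are independent and that the run-in is separate from the 10. A regimen with a 30% DLT rate then passes the run-in and enters the second stage with probability 0.420 × 0.882 = 37.1% at an ORR of 94%, and 0.420 × 0.318 = 13.4% at 78%.

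**4. What a boundary could do (illustration only, not a proposed cut-off).** Take a flag at 3 or more subjects with a DLT in the first 10, or 6 or more in the first 21 (10 plus half of 22), with p = 0.30.

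- *Run-in six separate.* P(3 or more of 10) = 0.617. Reaching the flag only at 21 adds 0.0282 × 0.0782 + 0.1211 × 0.2103 + 0.2335 × 0.4304 = 0.128. The total is 74.5%. Passing the run-in and then going unflagged: 0.420 × (1 − 0.745) = 10.7%.
- *Run-in six counted in the 10 and the 21.* After a passed run-in the six contain 0 DLTs with probability 0.28, or 1 with probability 0.72. The flag at 10 fires with probability 0.28 × 0.0837 + 0.72 × 0.3483 = 0.274. The look at 21 adds 0.0672 × 0.0782 + 0.2881 × 0.2103 + 0.3704 × 0.4304 = 0.225. The total is 50.0%. Unflagged: 0.420 × (1 − 0.500) = 21.0%.

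At a true rate of 10%, the same boundary pauses accrual unnecessarily 7.5% of the time (separate) or 2.7% (included, given a passed run-in).

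**The case against.** A reader might infer that, after the run-in, only a related death can pause the trial. The documents do not support that. The DSMB reviews safety data at the point where the decision to proceed is taken. Stage I futility can stop the study. Section 15 lets the investigator terminate at any time, and the supplier on a known or perceived risk to subjects. Serious events also go to the FDA, the IRB and the supplier, and Section 11.4.3.6 requires at least monthly exchange of case listings. These routes are real, so accrual would not necessarily continue through any number of non-fatal DLTs. They are, however, either discretionary or based on efficacy. None states how much non-fatal toxicity should prompt action.

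A reader might also infer that the Phase II gap produces the 42%. It does not. That figure belongs to the six-subject rule and is disclosed in Table 8. The gap means that no pre-specified non-fatal rule exists to catch those cases later.

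Nor does it follow that a toxic regimen would always accrue in full, as step 3 shows. Toxicity withdrawals are not replaced (Section 10.4). They could count against response if they stay in the denominator, which Section 10.3.2 leaves open.

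Finally, the gain from any boundary depends on whether the run-in six are counted, so quoting 74.5% alone would overstate it.

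**Conclusion.** The point holds in this form: after subject 6, a related death is the only pre-specified toxicity trigger. The DSMB report at 10 Phase II subjects carries no toxicity criterion, and none is scheduled for the 22 second-stage subjects.

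At a true DLT rate of 30%, the chance of passing the run-in is 42%. The 6.6 further subjects with a DLT among the 22 are conditional on the second stage opening and accruing in full. Both figures assume independent subjects and a constant rate; 30% is the rate that the protocol itself uses to read Table 8.

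Three textual matters belong with this:

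- The death trigger is one or more related or possibly related deaths in Section 10.5, but more than one related death in Section 8. These may be meant as a hold and then a discontinuation, but neither section says so.
- Section 11.4.5 gives the second stage as ten subjects, and Section 10.3.4 gives 22.
- The 10-subject report is tied both to enrollment and to the go/no-go decision. If it is prepared at enrollment, the latest subjects may not have completed the 28-day DLT window.

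**What to change.** 1. In Sections 10.5 and 11.4.5, have the sponsor, study statistician and DSMB pre-specify a Phase II accrual-hold boundary on the number of subjects with a DLT. Use the existing Section 10.2.4 definition and calibrate to the 10% and 30% rates that Section 10.2.6 uses to read Table 8. The cut-offs are theirs to choose.
2. Apply it at the existing 10-subject report and at one added second-stage report, each after the relevant subjects have completed Day 28.
3. State that any Section 10.5 hold is reported to the DSMB.
4. State whether the run-in six count among the 10 and the 32. Print the boundary's operating characteristics beside Table 8, both with and without them.
5. Reconcile the death triggers in Sections 8 and 10.5, and the second-stage size in Section 11.4.5 with that in Section 10.3.4.

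The cost is protocol wording, one extra report to an existing board, and a small chance of an unnecessary pause (about 3% to 7.5% at a 10% DLT rate with the illustrative boundary). No dose or individual treatment rule changes under items 1 to 4.
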